If a participant wishes to withdraw from the study, we will ask if the participant would like to continue in some but not all the research activities. If they would like to participate in only some of the research activities, we will note which ones and the participant will not be formally withdrawn from the study. If they wish to withdraw completely, a written withdrawal request is required and should be sent to the site PI (email preferred). The written request for withdrawal will be included in the participant's study record as documentation of the reason for removing a participant from the study. If a participant makes a verbal request and does not provide a written request, the verbal request will be documented by the study team member who receives the request and added to the participant's study record. Data that have been collected thus far will be analyzed.

ID: VIEW4E1B5231F800
Name: v2_Withdrawal of Participants

Privacy of Participants

If the study does not involve interaction with participants, answer "N/A" to the questions below.

- 1 * Describe how you will ensure the privacy of potential participants throughout the study (**privacy refers to persons and their interest in controlling access to themselves**):

Privacy will be ensured by making appointments with participants to call them or have a video conference about the study. This will ensure that participants will not be caught off-guard and feel pressured to take a study call in public. If the location is not adequately private, we will reschedule.

If a participant elects to come in, our clinical suites are located in a discrete laboratory in the School of Nursing.

- 2 * Describe the location where potential participants will receive research information and detail the specific actions the study team will take to ensure adequate privacy areas:

For phone calls and video conferences, we will set up an appointment with the participant to ensure that they can be in a location where they feel safe.

For in-person appointments, participants will learn about the study in a private consult or examination room in the UMGCCC or UMMS satellite location, other private room in the hospital, a clinical testing room in the Department of Pain and Translational Symptom Science (School of Nursing), or via telephone or video conference. After baseline assessments, the participant will be randomized and instructions will be given regarding the study activities for the next 13 weeks. This information will be similarly provided in a private room in UMGCCC or the School of Nursing or via the telephone or video conference. For in-person meetings, we will close the door and only the study staff and participant (and person(s) accompanying the participant, if desired) will be present; no members of the clinical care team or hospital staff will be present unless specifically invited by the potential participant.

- 3 * Describe potential environmental stressors that may be associated with the research:

There will be no more environmental stressors than typically experienced at a doctor's appointment. For phone and videoconferences, we will make appointments to ensure that the participant can plan to be in a comfortable location. For in person appointments, we will do what we can so that the room is comfortable to facilitate conversation regarding the study and its components (good lighting, comfortable temperature). We will make accommodations (as able and reasonable) for people with disabilities (e.g., comfortable place to sit, space to maneuver wheelchair, etc.).

- 4 * Will this study have a site based in the European Union?

Yes No

- 5 * Will the study have planned recruitment or data collection from participants while they are located in the European Union?

Yes No

Access link below for information about the EU General Data Protection Regulations to assist in answering these questions.

<https://www.umaryland.edu/oac/general-data-protection-regulation/>

Confidentiality of Data

- 1 * Will stored research data contain identifiers or be able to be linked to and identify individual participants (either directly or through a code/research ID)?

Yes

No, the data will be stored de-identified/anonymous (stripped of all identifiers, no way to identify individual participants)

- 2 * Where will research data be kept (address electronic and paper data as applicable)? (If this is a VA study please list specific sites that data will be kept.)

Electronic data, including POSTHOC data, REDCap data, and study team-created files, will be stored on HIPAA-compliant UMB servers.

Paper data will be stored in a locked filing cabinet in [name] laboratory/offices in the School of Nursing.

The audiorecorder will be stored in a locked cabinet in [name] laboratory/offices in the School of Nursing; files will be deleted as soon as they are transferred to the computer.

- 3 * How will such data be secured?

Paper-based data will be stored in a locked cabinet in [name] office in the Department of Pain and Translational Symptom Science in the School of Nursing. Questionnaire data will be collected via REDCap. Electronic data will be stored on a UMB-issued computer as part of [name] lab in the School of Nursing. The School of Nursing is secured by electronic key cards and a security guard at the front desk. [name] and her coordinator's personal offices are secured by traditional keys; [name] file cabinet is secured by a unique traditional key; and computers in [name] lab are password-protected. Electronic research records are stored on UMB's password-secured and firewall-protected networks. These are the same methods of security used for patient medical records. POSTHOC app data will be stored in a HIPAA-compliant server at UMB. All study data will be kept for at least six years after the study and all reports and publications are complete.

- 4 * Who will have access to research data?

Only members of the study team will have access to the stored data. All individuals who have access to the data will need to complete human research participant training as required by UMB.

Any investigator who is not on the study team and would like access to de-identified data must submit a request to the study chair (i.e., [name]) via a written request (e.g., email). If [name] considers the project appropriate, she will approve a release of the data and transfer it in a safe, HIPAA-compliant manner according to UMB rules (e.g., data use agreement if outside UMB).

To clarify, the POSTHOC app will pull activity data from the Fitbit app, but POSTHOC data will not be shared with or synced with the Fitbit app; therefore, none of our data will be shared with Fitbit/Google.

Also to clarify, the POSTHOC app does not connect with the participant's electronic medical record.

- 5 * Will study data or test results be recorded in the participant's medical records?

Yes No

- 6 * Will any data be destroyed? (Please note that data for FDA regulated research cannot be deleted however, VA data must be destroyed according to the VHA Records Control Schedule (RCS) 10-1)

Yes No

- 6.1 If Yes, what data (e.g., all data, some recordings, interview notes), when and how?

Audio-recordings of exit interviews will be transferred to the computer and then deleted off the recording device.

- 7 Do you plan to obtain a Certificate of Confidentiality?

Yes No

- 7.1 If Yes, upload your Certificate of Confidentiality. If you have not yet obtained the Certificate, please note that once it is obtained, you will need to submit an amendment to attach the document, make any needed changes to the submission and make needed changes to the Informed Consent Document.

Name

 CoC(0.01)

Created

10/21/2022 3:29 PM

Modified Date

10/21/2022 3:29 PM

- 8 * Discuss any other potential confidentiality issues related to this study:

We will only collect the data we need to answer the research question(s) and no superfluous data. Presentation of data in the form of posters, presentations, grant applications, and manuscripts, either in private or public settings, will not have any identifiable information.

Fitbit has been used in more than 1400 research studies (<https://healthsolutions.fitbit.com/research-library/>). Fitbit will only have access to any personal health information and personally identifiable information that the participant provides, and it is not necessary that they provide any personal information for the purposes of this study. For example, if they want to make up an anonymous email address for the purposes of this study alone, they can. Data (e.g., daily step counts) are private unless they choose to share them with friends as part of Fitbit communities. The Fitbit app will not have access to any study data other than what the Fitbit device collects, e.g., no information about medical history. Fitbit has security features to ensure that users' data are safe, for example two-factor authentication. We as study staff will not restrict use of any of the features of the Fitbit device such as sharing data within Fitbit "communities," and it will be up to the participant to decide how many other features they would like to use, and how they would like to use them.

The POSTHOC app will be vetted through Android and Apple procedures, which include customer safety of data, before they will be available for download. At this stage in development, the POSTHOC app will not be available to the public, only for this specific study. It will be hosted on UMB servers and Charles River Analytics will not have access to any participant data from the app or otherwise. No other apps will be able to "see" data that are in the POSTHOC app.

Monitoring Plan Selection

1 * Type of data safety monitoring plan for the study:

- Will use/defer to the external sponsor's Data Safety Monitoring Plan
- Data Safety Monitoring by a Committee**
- Data Safety Monitoring by an Individual
- There is no data safety monitoring plan in place

ID: V1EW4E1B00E30D400
Name: v2_Monitoring Plan Selection

Monitoring Plan - Committee

You indicated that the monitoring will be done by a Committee.

1 * Will the Committee be Internal or External?

- Internal DSMB
- External DSMB

2 * What data will be reviewed?

- Adverse Events
- Enrollment Numbers
- Patient Charts/Clinical Summaries
- Laboratory Tests
- Medical Compliance
- Procedure Reports
- Raw Data
- Outcomes (Primary, Secondary)
- Preliminary Analyses
- Other

2.1 If Other, specify:

3 * What will be the frequency of the review?

- Annually
- Bi-Annually
- Other

3.1 If Other, specify:

4 * Safety monitoring results will be reported to:

- IRB
- GCRC
- Sponsor
- Other

4.1 If Other, specify:

Monitoring Plan - Internal DSMB

You indicated that the monitoring committee will be an internal DSMB.

1 * List Internal DSMB Members:

Name

[View [name], RN](#)

[View [name], BS](#)

[View [name], MS](#)

[View [name]](#)

[View [name], OCN](#)

[View [name], PhD](#)

[View [name], PhD](#)

[View [name], MBA](#)

[View [name]](#)

[View [name]](#)

[View [name]](#)

[View [name], PhD](#)

[View [name]](#)

[View [name]](#)

[View [name]](#)

2 * Confirm that no financial or other conflicts of interest exists for the above individuals.

Yes No

3 * Will there be an interim efficacy analysis?

Yes No

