13. System Usability Scale (SUS) (6 weeks and post-intervention interview only): The System Usability Scale (SUS) is a simple questionnaire giving a global view of subjective assessments of usability. It offers a quick and simple to use questionnaire designed to assess the usability of a particular device or product. The SUS consists of ten usability statements that are rated on a Likert scale of 1 (strongly agree with statement) to 5 (strongly disagree with statement). Answers are coded and a total usability score is derived for the product or device under analysis. The questionnaire also includes an optional free-response comments area.

The self-administered questionnaires that will be completed at Week 0, Week 6, and Week 12 should take approximately 35-50 min in total to complete.

Dietary intake

Dietary intake will be assessed once at baseline, week 6, and week 12. It could occur at the same time as the biweekly check-in or another day that week. The ASA24® Dietary Assessment Tool is a freely available web-based tool used for epidemiologic, interventional, behavioral, or clinical research that enables multiple automatically coded 24-hour dietary recalls. It will be administered by a trained nutritionist via telephone or video conference and takes approximately 30-45 minutes.

Exit interview

After completion of the study (or earlier if a participant withdraws early from the study), a member of the study team will conduct an exit interview to understand the participants' experience of being in the study. We will ask them what they liked about the study, did not like about it, what features they liked/did not like about the POSTHOC app (for those in the intervention arm), if they would recommend the study to others, etc. This interview will be audio-recorded with explicit permission at the time of the interview, then transcribed for qualitative and mixed methods data analysis.

2. * Describe all procedures already being performed for diagnostic or treatment purposes (if not applicable to the study, enter "N/A"):

N/A
3. * Describe the duration of an individual participant's participation in the study:

Participants will participate in the study for approximately 14 weeks, including consent, baseline assessments, a 12-week intervention, and an exit interview.
4. * Describe the amount of time it will take to complete the entire study:

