Analysis plan for Aim 2. Our data from Aim 2 will provide estimated effect sizes to inform the sample size of a confirmatory Phase III RCT, per clinical trial guidelines (Freidlin et al., 2012). Our planned sample size is 54 participants total (36 in the POSTHOC group, 18 in the control group); we factor in 15% missing data to yield evaluable data from 46 participants total (31 for POSTHOC, 15 for control). Hypotheses will be tested at $\alpha=0.15$ (2-tailed) as appropriate for Phase I/II studies of this size (Rubinstein et al., 2005).

Aim: Obtain a preliminary estimate of the effect of the POSTHOC app vs. usual care on cumulative patient-reported symptom burden from the MD Anderson Symptom Inventory (MDASI).

Analysis plan: Cumulative severity is the sum of the individual severity levels from the 13 core symptoms from the MD Anderson Symptom Inventory (ranging 0-130). We will use the analysis of covariance (ANCOVA) with cumulative severity at Week 6 as the outcome, study arm (POSTHOC app vs. usual care) as the main independent variable and cumulative symptom severity at Week 0 as a covariate. In case of significant imbalance in other factors between arms (e.g., age), we might include additional covariates in the model. We chose Week 6 as the primary time point because preliminary data from our group shows greater benefits of behavioral interventions at 6 vs. 12 weeks ([name] et al., in preparation). Similar ANCOVA models will evaluate the effects of the POSTHOC app vs. usual care for each outcome at Week 6 and Week 12. To evaluate the longitudinal trajectory of each outcome, we will use repeated measures linear mixed model (LMM) incorporating the specific outcome at all three time points and using a linear contrast to test effects of POSTHOC app vs. usual care. We will use the intent-to-treat principle.

Analyses for Aim 3 and the Exploratory Aims that evaluate symptoms and feelings are analogous to Aim 2, using ANCOVA and LMM to assess the effects of the POSTHOC app vs. usual care control on each outcome. Exploratory analyses will include tests of moderation effects on the POSTHOC app by physical activity adherence, sex, age, etc.

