If the questions below are not applicable to the research (i.e., chart review), enter "N/A".

- 1 * Describe anticipated circumstances under which subjects will be withdrawn from the research without their agreement:**
The participant can be removed from the study by the investigator or sponsor. A participant may be withdrawn from the study if their disease becomes worse or if their doctor feels that staying in the study is harmful to the participant's health. The study team also holds the discretion to withdraw a participant from the study if their participation becomes harmful to a study team member. It is unlikely but possible that the entire study may be stopped by the sponsor, the investigator, the Institutional Review Board, the facility where the study is being carried out, or the University. In that case, participants' participation will end.

If a person is eligible and begins the study, and then becomes ineligible for any reason (e.g., surgery is scheduled during the study), they will be able to continue participation if they want to and their medical provider deems participation safe.

- 2 * Describe procedures for orderly termination:**
Upon completion of data collection, each participant will be thanked for their participation in the study, allowed to keep the activity tracker gratis, provided with their study data upon request, and compensated for their time.

If a participant withdraws (or is withdrawn) before the end of the study, they will be paid for the data they have provided, and the study team will not contact the person anymore. A 10-20% withdraw rate is built into the study design and recruitment goal, so there should not be a need to replace participants who withdraw before completing the study.

- 3 * Describe procedures that will be followed when subjects withdraw from the research, including partial withdrawal from procedures with continued data collection:**

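### Participants withdrawn by the study for worsening disease are not contacted again, so later symptom scores that are likely to be high go uncollected in an analysis called intent-to-treat

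*Combined protocol and SAP*

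**What the plan says.** Withdrawal of Participants, item 1, lists the circumstances in which someone can be removed without agreeing to it. One is disease progression: "A participant may be withdrawn from the study if their disease becomes worse". The same item takes a different line on people who become ineligible after starting, for example because surgery has been scheduled: "they will be able to continue participation if they want to and their medical provider deems participation safe".

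Item 2 covers what follows. It opens "If a participant withdraws (or is withdrawn) before the end of the study", so it applies to removals by the study as well as to voluntary exits, and it says that "the study team will not contact the person anymore".

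Item 3 describes partial withdrawal with continued data collection, but only on the participant's initiative: "If a participant wishes to withdraw from the study, we will ask if the participant would like to continue in some but not all" of the research activities. It closes with "Data that have been collected thus far will be analyzed".

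In the Analysis plan for Aim 2 (Sample Size and Data Analysis, item 2), the outcome is the 13-item MDASI severity sum (0 to 130). The primary analysis is an ANCOVA at Week 6 adjusted for Week 0, with further ANCOVAs at Week 12 and a mixed model over all three time points. The plan adds "We will use the intent-to-treat principle". The Missing data paragraph tabulates reasons by arm and leaves the method to be chosen once the amount missing is known. It gives likelihood-based weighting and multiple imputation as examples.

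**The concern.** The endpoint is symptom burden, and worsening disease can be expected to raise it. The rule therefore stops outcome collection for a reason tied to the outcome, even for someone who would have been willing to go on answering. The 15% allowance for missing data covers how many values are lost, not which ones.

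Likelihood methods and multiple imputation, in their standard form, assume that the observed data explain the missingness. Week 0 and any earlier scores may reduce the bias here, but a deterioration that begins after the last recorded score is not captured by them. No sensitivity analysis for outcome-related missingness is named.

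Balanced loss cannot be taken for granted. Removal is discretionary, the trial is open-label, and neither the principal investigator nor the coordinators are blinded. Usual-care participants have only the light data-collection app, so for them being withdrawn mostly means the end of measurement and check-in calls.

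Aim 2 is meant to supply the effect size for sizing a Phase III trial, so a distorted estimate would carry forward.

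**Working it through.** **Step 1. Follow a participant removed for worsening disease.**

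- Removed before completing Week 6: Week 0 is kept, there is no Week 6 value, and so there is no outcome for the primary ANCOVA.
- Removed between Weeks 6 and 12: the primary value is kept under item 3, and Week 12 is missing.
- In neither case does any section provide for a later MDASI, because item 2 ends contact and item 3's offer applies only to people who ask to leave.

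**Step 2. Reproduce the plan's own figures.** Evaluable numbers after 15% missing: 54 × 0.85 = 45.9 (46), 36 × 0.85 = 30.6 (31) and 18 × 0.85 = 15.3 (15). These match the plan. The whole allowance is thus 36 − 31 = 5 POSTHOC participants and 18 − 15 = 3 controls. Target difference: 0.50 × 17.04 = 8.52 points, as stated.

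**Step 3. Formula.** Let f1 and f0 be the shares lost in the POSTHOC and control arms. Let D be how many points higher the lost participants would have scored than those observed in the same arm, beyond what Week 0 explains. The full-arm mean is the observed mean plus f × D, so each observed mean is too low by f × D. Hence

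bias in (POSTHOC − control) = −(f1 − f0) × D.

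Lower scores are better, so a negative bias overstates benefit and a positive one understates it.

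**Step 4. Numbers.** The documents give neither a rate of worsening nor the scores of those removed. I assume D = 0.5, 1 or 2 SD (8.52, 17.04 or 34.08 points). The counts run from one person up to the whole missing-data allowance in an arm. Percentages are of 8.52.

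| Lost: POSTHOC of 36, control of 18 | D = 8.52 | D = 17.04 | D = 34.08 |
|---|---|---|---|
| 0, 1 | +0.47 (5.6%) | +0.95 (11.1%) | +1.89 (22.2%) |
| 0, 3 | +1.42 (16.7%) | +2.84 (33.3%) | +5.68 (66.7%) |
| 1, 0 | −0.24 (2.8%) | −0.47 (5.6%) | −0.95 (11.1%) |
| 5, 0 | −1.18 (13.9%) | −2.37 (27.8%) | −4.73 (55.6%) |
| 2, 1 | 0 | 0 | 0 |
| 5, 3 | +0.24 (2.8%) | +0.47 (5.6%) | +0.95 (11.1%) |

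Worked example: 3 of 18 controls at 2 SD gives −(0 − 3/18) × 34.08 = +5.68, and 5.68/8.52 = 66.7%.

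The row with 2 and 1 lost shows that equal shares (2/36 = 1/18) cancel in the difference, although both arm means are then too low.

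**The case against.** Much can be said for the plan. Removal is permitted, not required. The documents do not say how often it will happen, and a population treated with curative intent suggests few cases. Item 3 keeps scores already recorded, so only removals in roughly the first six weeks touch the primary value. The rule on becoming ineligible may keep some people in: the sole exclusion criterion is planned surgery, radiotherapy or chemotherapy, so a participant whose worsening leads to such treatment could fall under it. Research Related Risks adds that nobody is withdrawn for leaving study activities undone. Reasons for missing data are tabulated by arm, and baseline adjustment and the mixed model use the earlier scores. This is a small phase I/II trial seeking a preliminary estimate. All of that stands, and it limits the size of the problem. It does not supply the missing assessments.

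A reader might infer three stronger things that the documents do not support:

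- **That the highest scores in the trial are certain to be lost.** High scores are a reasonable expectation, but nothing in the documents records them.
- **That intent-to-treat analysis becomes impossible.** Participants can still be analysed as randomized. The result then rests on assumptions about the missing values.
- **That the exit interview contradicts the no-contact rule.** It is planned after completion, "or earlier if a participant withdraws early from the study", and can be read as taking place at exit, before contact ends. It does not collect the MDASI in any case.

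**Conclusion.** The point holds as a gap in follow-up. The withdrawal rules end outcome collection for people removed because their disease worsened, while people who ask to leave are offered continued assessment. The item 1 rules on worsening disease and on continuing after becoming ineligible also need to be reconciled, since one participant could fall under both.

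The effect may be nil or material. On the assumed gaps of 0.5 to 2 SD, one-sided loss understates benefit by about 6% to 67% of the target if it falls on controls, and overstates it by about 3% to 56% if it falls on POSTHOC. The upper ends require the whole missing-data allowance in one arm to consist of such removals, with none in the other, and a 2 SD gap. If both arms used their full allowance this way, the bias would be about 3% to 11%.

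The documents do not settle the direction, and a reader should not infer that the rule favours the app. The case for changing it is that values not collected cannot be recovered later and collecting them costs little.

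**What to change.** Separate stopping the intervention from stopping data collection.

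- In item 3 of Withdrawal of Participants, extend the offer of partial participation to people withdrawn by the study. Ask them whether they will still complete the MDASI at Weeks 6 and 12 by REDCap.
- In item 2, limit the end of contact to people who decline, people who withdraw consent to data collection, and people for whom the treating doctor or the study team considers further contact harmful. The last exception covers the harm and staff-safety grounds in item 1.
- State how this fits with the item 1 rule on continuing after becoming ineligible.

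The decision to withdraw someone from the intervention stays as written.

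The cost is protocol wording, possibly a line in the consent form, and a few extra questionnaires that Surveys/Questionnaires puts at 2 to 4 minutes each. The downside is a slight burden on people who have become ill. Some will decline, so the gap will shrink but may not close.
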